7.2.2. Other Secondary Endpoints

All time-to-event endpoints start from the day of randomization. The following variables will be analyzed:

- Proportion of subjects who maintained Clinical Response at Week 8 and Week 24 of the RW period, respectively
- Percentage of days with no or minimal pain (pain ≤ 2 on the 11-point NRS) in the first 8 weeks and 24 weeks of the RW period, respectively
- Proportions of subjects with absent or minimal pericarditis symptoms (based on the 7 point rating scale of PGIPS) at Week 8 and Week 24 of the RW period, respectively
- Proportion of subjects without pericarditis recurrence in the first 24 weeks of the RW period
- Time to pericarditis pain NRS ≥ 4
- Time to CRP level ≥ 1 mg/dL. This is for elevation of CRP for which no other cause other than pericarditis was identified.
- Time to pericardial rub
- Time to widespread ST-segment elevation or PR-segment depression on ECG, whichever occurs first
- Time to new or worsening pericardial effusion on ECHO
- Change in category of ECHO pericardial effusion size at week 24 and end of RW based on central labs
- Change over time in CRP levels
- Change over time in the subject's assessments of pericarditis pain (weekly average)
- Proportion of subjects with absent or minimal pericarditis activity based on the PGA-PA over time

- Proportion of subjects with absent or minimal pericarditis activity over time based on the PGIPS over time
- Change over time in SF-36 Physical and Mental Component Scores and domain scores (Physical Functioning, Role-Physical, Bodily Pain, General Health, Vitality, Social Functioning, Role-Emotional, and Mental Health domains)
- Changes in SF-6D, 6 domain scores and utility index
- Change in EQ-5D-5L. There are 6 questions in this instrument (Section 6.2.1.8). Each of the first 5 questions has 5 levels, from level 1 (best) to level 5 (worst). They are mobility, self-care, usual activities, pain/discomfort, and anxiety/depression. The sixth question is the health on the day, from 0 (the worst) to 100 (the best) (van Reenen and Janssen 2015). The levels of the first 5 questions (EQ-5D-5L profile) will be converted to an index value. Change from baseline in each one of these 7 values will be an endpoint.
- Change in subject's sleep quality assessed with the ISI (Section 6.2.1.9). There are 7 items in the ISI. Change in ISI total score, which is the sum of the 7 items over time, will be the endpoint.
- Change in ISI categories. The ISI total scores are divided to 4 categories:
 - 0–7 = No clinically significant insomnia
 - 8–14 = Subthreshold insomnia
 - 15–21 = Clinical insomnia (moderate severity)
 - 22–28 = Clinical insomnia (severe)
- Cumulative number (percentage) of subjects who received sequential ORT, prednisone, or bailout rilonacept for pericarditis period every 4 weeks cumulatively in the RW period
- The following endpoints are for subjects enrolled in the MRI substudy. There will be no hypothesis testing performed. Only summary statistics will be provided.
 - Proportion of subjects with pericardial Delayed Hyperenhancement at RW baseline and week 24 based on the MRI assessment
 - Proportion of subjects with Myocardial Delayed Hyperenhancement at RW baseline and week 24 based on the MRI assessment
 - Proportion of subjects with pericardial Effusion and Effusion size at RW baseline and week 24 based on the MRI assessment

7.3. Other Endpoints

These include efficacy endpoints in the RI period and the LTE. Since there is no control arm in these 2 periods, only descriptive statistics will be provided. All time-to-event endpoints start from the day of receiving rilonacept in that period.

The annualized event rate for recurrence of pericarditis will be calculated for the combined RW and LTE periods.

7.3.1. Efficacy Endpoints for the RI Period

The following efficacy endpoints are included in this period:

- Time to pain response. Pain response is defined as a rolling average of NRS score of 2 or less on three consecutive days
- Time to CRP normalization (≤ 0.5 mg/dL)
- Time to monotherapy
- Time to clinical response (monotherapy + NRS ≤ 2 + CRP ≤ 0.5 mg/dL)
- Proportion of subjects who achieved Clinical Response at the RI Week 12. Clinical Response is defined as reaching monotherapy on or before week 10 and a weekly average of daily pericarditis pain of ≤ 2.0 on the 11-point NRS and CRP level ≤ 0.5 mg/dL at the RI Week 12/RW baseline visit.
- Number (percentage) of subjects with normalization of CRP at RI Week 12
- Change from baseline in pericarditis pain at RI Week 12 and over time
- Change from baseline in CRP level at RI Week 12 and over time
- Resolution of ECHO and ECG abnormalities (yes/no) at RI Week 12
- Percentage of days with no or minimal pain while on treatment
- Proportion of subjects with absent or minimal pericarditis symptoms based on PGIPS over time
- Proportion of subjects with absent or minimal pericarditis activity based on the PGA-PA over time
- Change over time in the SF-36 Physical and Mental Component Scores and domain scores
- Change in the SF-6D 6 domain scores and the utility index
- Change in the EQ-5D-5L (Section 7.2.2 contains details about calculation)
- Change in the subject's sleep quality assessed with the ISI (Section 7.2.2 contains details about calculation)
- Change in ISI categories
- Number (percentage) of subjects who were off background pericarditis medication on or before weeks 4, 8, 10, and 12

7.3.2. Efficacy Endpoints for the LTE Period

Efficacy endpoints for the LTE will be defined in the Statistical Analysis Plan.

7.4. Sample Size Calculations

For the purpose of sample size estimation, time to pericarditis recurrence is assumed to follow an exponential distribution. An event of interest is defined as a subject's first adjudicated recurrence of pericarditis. The following assumptions are used in the sample size calculation using EAST 6.4.1:

- 1-sided significance level 2.5%
- Power 90%
- Median time to event (in weeks) in placebo 8
- Hazard ratio (rilonacept/placebo) 0.244
- Percentage of subjects in the RI period that will not reach RW 10%

Given these assumptions, a total of 22 adjudicated pericarditis recurrence events is required to achieve the power. About 25 subjects per arm (a total of 50 subjects) will be randomized. Considering 10% of subjects in the RI period that will not reach the RW period, approximately 56 subjects will be enrolled in this study.

Patient enrollment and the pericarditis recurrence event accrual will be closely monitored during the study. The monitoring activities will be done in a blinded fashion during the RW period. If the number of patients randomized is less than 50 and/or the time anticipated for the number of events required for the analysis of primary efficacy endpoint significantly exceeds the projected timeline, additional patients may be enrolled and/or randomized at Kiniksa Pharmaceutical's discretion. However, at this time it is anticipated that no more than 100 subjects will be enrolled into this study.

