3.1.3. Double-blind Placebo-controlled RW Period (pericarditis recurrence event-driven duration)

During the RW period, subjects who were able to stop background pericarditis medications and who achieve Clinical Response on rilonacept monotherapy at RI Week 12/RW baseline will be randomized 1:1 to double-blinded administration of study drug:

- Rilonacept 160 mg (or 2.2 mg/kg in pediatric subjects ≥ 12 and < 18 years old) SC injections once weekly OR
- Matching placebo SC injections once weekly

Pericarditis Recurrence in the RW Period: For the definition of pericarditis recurrence, refer to Section 6.2.3.

Upon pericarditis recurrence, subjects who report at least 1 day with pericarditis pain measurement ≥ 4 on the 11-point Numerical Rating Scale [NRS] and have 1 CRP value ≥ 1 mg/dL (either on the same day or separated by no more than 7 days) will receive **bailout rilonacept** (2 open-label injections of 160 mg rilonacept [or 4.4 mg/kg for pediatric subjects]) irrespective of randomized treatment assignment and as soon as at least 5 days have passed since the last study drug injection. The subjects transitioning to bailout rilonacept will remain blinded to their prior RW period treatment assignment. Sequential Oral Rescue Therapy (ORT), i.e., analgesics first, then NSAIDs, and then colchicine, can be added, if needed, at the discretion of the Investigator, as outlined in Section 5.6.3 and detailed in the Pharmacy Manual.

Subjects with pericarditis recurrence who do not meet the protocol criteria for bailout rilonacept will continue blinded study drug until they meet the protocol criteria for bailout rilonacept or through the end of the RW period. For those subjects, sequential ORT can be added to blinded study drug at the discretion of the Investigator, as outlined in Section 5.6.3 and detailed in the Pharmacy Manual.

All suspected pericarditis recurrence events in the RW period will be formally adjudicated by the Clinical Endpoint Committee (CEC), and only events that are confirmed by the CEC as pericarditis recurrences will be used in the Primary Endpoint analysis.

The RW period will continue until the prespecified number of primary efficacy endpoint (CEC-confirmed pericarditis recurrence) events has occurred. Based on projected event accrual and subject randomization, Kiniksa Pharmaceutical will determine the end of the RW period and announce to sites so that subject End of Randomized Withdrawal (EORW) visits

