3.1.4. Long Term Extension Treatment Period (LTE) (up to 24 months)

Upon completion of the RW period and the EORW visit, all subjects that did not discontinue study drug will have an option to continue treatment with open-label rilonacept in the LTE or to withdraw from the study. Subjects still in the RI period at the time that the RW period has ended and the LTE is opened will have the option to enter the LTE directly when they have completed the RI period and have met the definition of clinical response or to withdraw from the study.

Treatment in the extension period may continue until the earliest of the following dates:

- Rilonacept is approved for commercial use or is available for reimbursement to treat pericarditis in the region
- The subject has received 24 months of treatment in the LTE or the Investigator and subject decide to continue in the study off-treatment
- Additional reasons for discontinuation of treatment can be found in section 4.3.1.

Any subject who, in the opinion of the Investigator, should not continue open-label rilonacept will be withdrawn from the study.

Subjects will be reviewed again at 18 months after their most recent recurrence, (i.e., the qualifying episode for their original study enrollment prior to enrolling in the RI period or a recurrence in RW which was treated with bailout rilonacept, whichever is the later). During this visit, the Investigator and subject will decide whether to continue treatment with open-label rilonacept, to continue in the study off-treatment for observation and rilonacept bailout upon subsequent recurrence, or discontinuation from the LTE. This review may be supplemented by cMRI and/or echocardiogram and/or additional diagnostic testing as determined by the Investigator. Subjects may also be unblinded at that time (if available) at the request of the Investigator per procedures outlined in the Unblinding Plan to assist in clinical decision-making.

[figure not shown]
Subjects completing the RW period are projected to be dosed with rilonacept for a minimum of approximately 36 weeks and a maximum of 2 years based on enrollment assumptions and pericarditis recurrence events accrual time. Subjects who enter the LTE will be dosed for up to 24-months longer.

Pericarditis Recurrence in the LTE Period (Observation arm)

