7.7.1. General Methods

Statistical analysis will be performed using SAS[®] software Version 9.4 or later. Continuous variables will be summarized using the mean, the standard deviation, median, minimum value, and maximum value. Time-to-event variables will be summarized using percent censored, event rate, and 25th, 50th, and 75th percentiles with 95% CI, if estimable.

Categorical variables will be summarized using frequency counts and percentages. Data will be listed in data listings.

At each of RI and RW periods and in the LTE, baseline will be the last value before the first dose of study drug within each individual period unless otherwise specified. For change-over-time endpoints in the RW period, by-visit analysis will be performed at each scheduled visit for at least 24 weeks.

The analysis for treatment comparison will be triggered after at least the 22nd CEC-confirmed pericarditis recurrence events have been accrued. At that time, randomization will be closed, and subjects will return to study sites for the EORW visit. At that point study treatment will stop (completing the database for the primary efficacy endpoint analysis), and subjects will either continue into the LTE or complete their study participation. Missing data due to end of RW period will be considered as missing at random. Handling of missing values will be described in the SAP.

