7.7.4. Analysis of Primary Efficacy Endpoint

Primary analysis of this study will be triggered after at least the 22nd CEC-confirmed pericarditis recurrence events have been accrued. The log rank test will be the primary method for the analysis of time to recurrence, stratified by the stratification variables for randomization. Detailed censoring rules will be described in the SAP.

A sensitivity analysis will be performed based on the Investigator's judgement of pericarditis recurrence. Additional sensitivity analyses may be defined in the SAP.

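### The stated 90% power at 22 events is the formula value for an unstratified test; the planned stratified log-rank has about 84% to 87% at exactly 22 events, and the projected 36-week minimum of rilonacept no longer follows from the event-driven design

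*Protocol*

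**What the plan says.** All references are to the current protocol, Version 3.0, unless stated.

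- **Planning inputs (Section 7.4).** "1-sided significance level 2.5"%, power 90%, "Median time to event (in weeks) in placebo 8", "Hazard ratio (rilonacept/placebo) 0.244", exponential times. The result: "a total of 22 adjudicated pericarditis recurrence events is required to achieve the power", with about 50 subjects randomized and 56 enrolled. Enrolment is anticipated not to exceed 100. Stratification is not mentioned.
- **Primary test (Section 7.7.4).** "The log rank test will be the primary method for the analysis of time to recurrence, stratified by the stratification variables for randomization". Section 7.7.2 names the factors, oral corticosteroid use and idiopathic diagnosis (each yes or no), so there are four cells. A stratum without events is pooled with its neighbour.
- **Trigger (Section 7.7.1).** "The analysis for treatment comparison will be triggered after at least the 22nd CEC-confirmed pericarditis recurrence events have been accrued". Randomization then closes and subjects return for the end-of-period (EORW) visit. Section 3.1.3 ends the randomized-withdrawal (RW) period on the event count, with no minimum duration.
- **Dosing projection (Section 3.1.4, repeated in the synopsis).** Subjects completing the RW period are projected to receive rilonacept for a "minimum of approximately 36 weeks and a maximum of 2 years".

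**The concern.** Section 7.4 presents 90% as the power delivered by 22 events. The formula behind that figure describes an unstratified test and is optimistic when the effect is very large and events are few: at a hazard ratio of 0.244 the placebo risk set empties quickly. Spreading 22 events over four cells costs more.

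Under Version 2.0 this mattered little, because every subject in the RW period also had to be treated for 24 weeks, and its Section 7.4 noted that actual power could therefore be higher. Version 3.0 removed the 24-week rule and that remark and kept 22 events. Its summary of changes gives as the reason that the study is powered for time to event, so the stated power now carries the justification alone.

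The dosing projection has the same origin. A minimum that most subjects would miss misinforms sites and ethics committees about exposure, although it does not touch the primary test.

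**Working it through.** **1. Reproducing 22 events.** Schoenfeld's formula, 1:1 allocation:

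- events = 4 × (1.960 + 1.2816)² / (ln 0.244)² = 4 × 10.507 / 1.990 = 21.1, rounded up to 22.
- power at 22 = Φ(√22 × 1.4106 / 2 − 1.960) = Φ(1.348) = 91.1%.
- enrolment = 50 / 0.9 = 55.6, rounded up to 56.

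The plan's figures reproduce. Freedman's formula shows how much the approximation matters at this effect size:

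- events = (1.244 / 0.756)² × 10.507 = 28.5.
- power at 22 = Φ(√22 × 0.756 / 1.244 − 1.960) = Φ(0.890) = 81.3%.

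**2. Power of the planned test, by simulation.** From the protocol: exponential times, medians 8 and 8 / 0.244 = 32.8 weeks, 1:1 allocation, 1-sided 0.025, four strata. Assumed, because the protocol does not give them: uniform accrual over 0, 26, 52 or 78 weeks; 50, 75 or 90 randomized; stratum mix from equal to very uneven; permuted blocks of 4; the same hazard in every stratum. The cutoff is at exactly the 22nd event, with 5,000 to 8,000 runs per scenario (Monte Carlo standard error about 0.4 to 0.5 points). Selected results:

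| Randomized, accrual | Strata (%) | Unstratified | Stratified | Stratified with pooling rule |
|---|---|---|---|---|
| 50, 26 wk | 45/40/8/7 | 88.0% | 85.3% | 85.5% |
| 50, 52 wk | 45/40/8/7 | 87.8% | 84.3% | 84.6% |
| 50, 52 wk | 25 each | 87.7% | 83.8% | 83.8% |
| 50, 52 wk | 50/44/3/3 | 88.2% | 85.0% | 85.5% |
| 90, 52 wk | 45/40/8/7 | 87.6% | 84.9% | 85.1% |

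Across all scenarios stratified power ran from 83.8% to 87.3%; the highest values came from simultaneous entry. In the second row, the step from formula to simulated unstratified test is 91.1 − 87.8 = 3.3 points, and stratifying takes a further 87.8 − 84.3 = 3.5.

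**3. Events needed.** In the same scenario, stratified power is 87.7% at 24 events, 89.1% at 25, 90.0% at 26 and 91.6% at 27.

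**4. Effect of a wind-down.** If randomization closes at the 22nd event but events keep counting until EORW visits, stratified power was 84% with no lag, 86% to 87% at 2 weeks, 87% to 88% at 3 and 89% to 90% at 4 (2,500 runs, standard error about 0.7 points). A further check gave 87% to 90% for lags of 2 to 4 weeks. The protocol does not state the lag.

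**5. What the 24-week rule added.** With 50 randomized over 52 weeks, it would have produced about 40 events and 99% stratified power.

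**6. The dosing minimum.** 12 run-in weeks + 24 RW weeks = 36. Under the same hazards, the share of randomized subjects with less than 24 weeks in the RW period at the 22nd event is about 59% (50 over 52 weeks) to 66% (90 over 78 weeks), and 45% to 100% over all accrual patterns tried. The protocol itself expects short follow-up: Section 3.1.2 provides for subjects still in run-in when the RW period closes, and Section 7.5 defines separate sets for subjects randomized at least 8, 16 or 24 weeks before cutoff. Subjects are "randomized 1:1 to double-blinded administration of study drug", so a placebo subject without bailout receives rilonacept only in the 12-week run-in.

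**The case against.** **No arithmetic slip.** The count of 22 and the enrolment of 56 both reproduce, and sizing on the unstratified formula while testing with the stratified log-rank is ordinary practice. This stands. A reader might infer that the event count was miscalculated; the documents do not support that.

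**A cut at exactly 22 is the worst case.** The trigger is at least 22 events, the sponsor announces the end of the RW period, EORW visits follow with a window of 7 days either way, and some events may be awaiting adjudication when the 22nd is confirmed. This stands in part. A few extra events would close much or nearly all of the gap, so a type II error of 15% should not be read as a fixed property of the design. But nothing guarantees those events.

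**Assumed inputs.** Accrual, stratum mix and block size are not in the protocol, and equal hazards across strata make stratification look purely costly. When corticosteroid use was made prognostic (hazard ratio 2 or 4 between strata), stratified power stayed near 85% while unstratified power fell to 86% or 78%. So the split of the loss in step 2 is not robust, and the result is no argument for dropping stratification. Stratified power at exactly 22 events stayed well below 90% in every scenario tried.

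**The 36 weeks is only a projection.** It is approximate, tied to enrolment and event accrual, and sets no treatment rule. True, but it is labelled a minimum, and the current design does not produce it.

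**Conclusion.** The point holds in two parts.

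- **Power.** The 90% is the unstratified asymptotic value. The planned stratified test has about 84% to 87% at exactly 22 events, and about 87% to 90% if 2 to 4 weeks of wind-down add events. These figures rest on the protocol's exponential hazards and on the assumed accrual, stratum mix and lag. Type I error and the validity of the test are unaffected.
- **Dosing.** The 36-week minimum contradicts the event-driven RW period and cannot hold for placebo subjects without bailout. This follows from the text and needs no simulation.

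A reader might also infer that the trigger must move to 26 events. It need not: the inaccuracy lies in what the protocol states, and restating it resolves the point.

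**What to change.** 1. **Section 7.4.** State that 22 events and 90% come from the unstratified log-rank approximation. Add that the planned stratified test has roughly 84% to 87% power at exactly 22 events, naming the accrual, stratum-mix and cutoff assumptions, once the sponsor's own simulation has confirmed the figure. If events up to the EORW visits are to count, say so and give the lag assumed. The cost is one short simulation and a text change.
2. **Synopsis (Estimated Study Duration) and Section 3.1.4.** Reconcile the projected minimum dosing with an RW period that has no minimum duration and a placebo arm. The cost is a text change.
3. **Optional.** If 90% is wanted for the planned test, a trigger at 26 CEC-confirmed events would provide it. Under the assumed accrual this falls about 3 to 5 weeks later (median cutoff moves from 23.7–42.0 to 26.4–47.2 weeks) and needs no enrolment above the 100 already anticipated.

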7.5. Analysis Sets

The following analysis sets will be used in the statistical analyses.

Intent-to-Treat (ITT) Analysis Set: All subjects who are randomized in the RW period will be included in the ITT analysis set. The primary analysis for efficacy endpoints in the RW period will be based on the ITT analysis set. Treatment comparisons for all ITT analyses will be based on each subject's treatment assignment from randomization.

ITT Week 24 analysis set: All subjects randomized at least 24 weeks before data cutoff will be included. This analysis set will be used for secondary efficacy endpoints measured at week 24 in the RW period.

ITT Week 16 analysis set: All subjects randomized at least 16 weeks before data cutoff will be included. This analysis set will be used for secondary efficacy endpoints measured at week 16 in the RW period.

ITT Week 8 analysis set: All subjects randomized at least 8 weeks before data cutoff will be included. This analysis set will be used for secondary efficacy endpoints measured at week 8 in the RW period.

Safety Analysis Set: All subjects who received at least 1 dose of study drug in the RI period will be included in the safety analysis set (SS). Safety analyses will be based on the actual treatment a subject received.

Run-in Analysis Set: All subjects who received at least 1 dose of study drug in the RI period will be included in the RI analysis set (RIS).

Run-in Week 12 Analysis Set: All subjects who received the first dose in the RI period at least 12 weeks before data cutoff. This analysis set will be used for secondary efficacy endpoints measured at Week 12 in the RI period.

Long Term Extension Analysis Set: All subjects who received at least 1 dose of study drug in the long-term extension period will be included in the long-term extension analysis set

Per-protocol Analysis Set: The per protocol (PP) analysis set is a subset of the ITT analysis set with the exclusion of subjects with major protocol violations or violations that may potentially bias statistical analyses or the ethical conduct of the study. The criteria of these violations will be determined prior to unblinding. This analysis set may be used for sensitivity analyses for efficacy endpoints in the RW period.

Pharmacokinetic Analysis Set: The PK analysis set includes subjects who receive at least 1 dose of study drug and have at least 1 PK sample. The PK analysis set will be used for all PK analyses.

